## SYNOPSIS

Title	Wearable eye-tracking device as means of communication in the critically ill, and mechanically ventilated patient
Short Title	Eye-Control Trial
Principal Investigator	[name], PhD Assistant Professor, Department of Neurology and Neurosurgery, Division of Neurocritical Care Emory University School of Medicine
Study Description	The study will have two steps: (1) safety and efficacy phase, in which we will enroll up to 60 patients, with main goal to experience the use of the device in critical care settings, and better prepare for the second part (burn-in period); (2) a randomized controlled trial that will treat eligible and consented patients with either EyeControl or the current standard of care from a communication stand point. On a daily basis, all patients admitted will be screened according to the predefined inclusion/exclusion criteria. Eligible patients (or their LARs) will be approached by the study team to obtain consent. Once enrolled, and randomized to the intervention arm, the patients will be instructed how to use the EyeControl device and will keep the device on for as long as they would like. While on, the device will collect data as a potential monitor, such as time of wakefulness, and will screen for delirium by CAM-ICU questionnaire. At six months, we will contact the patient to assess his functional and cognitive performance using standardized questioners. Following this interview, the patient will end the participation in the trial.
Purpose	To determine the safety, tolerability, and ease of use of the EyeControl device and determine impact on communication and delirium in critically ill, ventilated patients in the intensive care unit.
Design	This is a single-center, Phase 1/2, two-step prospective, open-label, blinded-endpoint (PROBE) study evaluating the tolerability and efficacy of the EyeControl device.
Objectives	To evaluate the efficacy of a wearable communication device in preventing and treating ICU-delirium in critically ill patients who are admitted to the intensive care unit (ICU) and mechanically ventilated. The study will assess the safety, tolerability, and ease of use of the EyeControl device; examine its potential monitoring capabilities; determine the change in level of frustration and discomfort following use of the device; and measure long-term outcome of these critically ill patients.
Study Population	Critically ill patients who are admitted to the ICU at Emory University Hospital (EUH) who require mechanical ventilation for at least two days and are awake enough and cooperative to attempt working with the communication device (defined as Richmond Agitation Sedation Scale (RASS) score of -1 to 1).
Enrollment / Duration	Step 1: 60 Patients, approximately 8 months – No Long-Term Outcomes Step 2: 244 Patients, approximately 12 months – With LTO extending to 6 months
Subject Inclusion	
 
• Intensive Care Unit (ICU) Admission
 
• Mechanically ventilated for at least 24 hours
 
• RASS between -1 to 1 at the time of screening (Note: minimal sedation is allowed including low-dose Fentanyl, Dexmedetomidine, Ketamine, Propofol, etc.)
 

Subject Exclusion	
 
• < 18 years of age
 
• Not admitted to the ICU
 
• Inability to follow commands during screening
 
• Known cerebral injury (acute or chronic) in the dominant hemisphere concerning for aphasia on clinical assessment
 
• Significant pre-existing neurologic (i.e., dementia and/or cognitive deficiencies), psychologic, or baseline communication challenges that would confound outcomes assessments (including hearing loss)
 
• Inability to blink or move eyes for any reason
 
• Prisoner or incarceration
 
• Inability or unwillingness to provide informed consent
 
• Unwillingness to be contacted for follow-up
 

Outcome Measures	
For the burn-in phase, the primary outcome will be time to successful operation of the device (see below for definition), and secondary outcomes include length, type and intensity of use (e.g. use for communication, entertainment, call for help etc), safety, and proof of concept of non-communication features of the device such as wakefulness time monitoring and CAM-ICU capturing.
 
The primary end point of the second step will be number of alive and delirium days while in the ICU and on the ventilator up to 14 days from randomization, or to extubation or ICU discharge, the earliest. Secondary endpoints will include: proportion of patients who were able to operate and use EyeControl, the specific parameters of successful patients compared to those who were unable to operate it; the length and intensity of use; the correlation between the monitoring data and clinical data; and the cognitive and functional long term outcomes as assessed by telephone by the Critical care, Brain Dysfunction and Survivorship (CIBS Center from Vanderbilt University).

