#### Secondary goals:

1. Assess the safety, tolerability, and ease of use of the EyeControl device; Specifically, we will assess on a daily basis for any adverse events related to the device. We will also document need for re-training on the device as a marker for ease of use.
2. Measure the length and intensity of use for communication and call for help; Intensity will be measured by the number of times the device is used and for which purpose as a categorical measure (eg, call for help, talk using predefined sentences, communicate using letter by letter dictation etc).
3. Correlate between the monitoring data and clinical data: the device will assess CAM-ICU independently, and a study team member will repeat this analysis and the documented results will be documented. We will also track any clinical decision making based on wakefulness time information (for example a decision to add melatonin agonist to promote sleep) ;
4. Measure the cognitive and functional long-term outcomes, by phone questioners, to be done in a blinded fashion at 6 months from ICU discharge.

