- b. Wakefulness monitoring—the device will record the times in which the patient is awake by monitoring when the patient's eyes are open. This data will later be correlated with outcome measures such as delirium, LOS, and functional outcome. Changes in wakefulness time will also be correlated with ICU interventions such as adding a melatonin-agonist to promote sleep.
- c. CAM-ICU validation—every shift, after the nurse and/or study team member assesses CAM-ICU, the device will repeat the test by using multiple-choice questions and ask the patient to choose the correct answers by blinking. We will later correlate the device's results with the nursing/study team ones.
- d. Reorientation – at a defined time interval, if the patient's eyes will be open, the device will read the patient the current date/time/location.
- e. Entertainment – patients will have the option to listen to music.
- f. Family communication – Families will be supplied with a patient-unique link to record audio messages which the patient will be able to listen to through the device.

To address the secondary goal of proficiency with device operation, we will administer a daily orientation questionnaire via the device. If a patient fails this proficiency check, study staff will perform a device re-training module. The frequency and amount of necessary re-training will be captured as another data parameter.

During the study, we will collect clinical information from the patient's chart including: demographics, diagnoses, use of sedatives or medications that could change cognitive function, nursing charting (including neurological assessment), laboratory results, days on the ventilator, procedures, discharge destination, mortality, and functional outcome. All of these will be taken into account for the final analysis of the study. For example, this data could help us better identify which patients used the device more than others and which could benefit from its monitoring properties apart from its communication function.

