As part of its operation, the device captures photographs and video of the patient's eyes (figure 3). In addressing the secondary goal of potential correlation between eye behavior and clinical events, we will explore this possibility by evaluating photographs of the eyes at the times of clinical events (i.e. hypoxia, new onset shock, or new onset sepsis). The device will activate the image data collection only after 50 consecutive frames of eye-in-the-image. This should be a safety index to verify that the device is only recording the eye. It will stop recording immediately when non-eye-in-the-image occurs. Data processing to decide if an eye is in the image is done locally on the device, so eventually only images of eyes should be collected. All external image data processing will be done following deidentification of the data, using the patient code only as an identifier.

Figure 3. Example photographs captured by the EyeControl device.

No randomization or blinding is planned for this step of the study, and no samples are planned to be collected.

---

**STEP 2: MEASURE REDUCTION IN DELIRIUM-FREE AND ALIVE DAYS IN THE ICU WITH EYECONTROL-BASED COMMUNICATION COMPARED WITH THE STANDARD OF CARE.**

The second step will be similar to the operation of the first one, in terms of patient screening and enrolling. The main difference will be the randomization process. Patients will be randomized to use EyeControl for as much as they wish, versus the standard of care. Randomization will be done centrally, and will be stratified to the specific unit, gender and age, race and ethnicity.

The primary goal of the second step will be to measure the time spent alive and non-delirious in the ICU with EyeControl-based communication compared with the standard of care. Delirium will be defined as CAM-ICU positive, starting at day 1 of use (following the day of training), up to 14 days from randomization or ICU discharge, the earliest. However, patients could require moderate to deep sedation following randomization, for example due to new or evolving medical complication. Whenever the RASS is below (-1), CAM-ICU will not be measured, and will be charted as undetermined. Therefore, only days in which the patient will be CAM-ICU positive, will be counted towards the primary outcome. CAM-ICU positive days prior to randomization will not be counted towards the primary outcome.

[figure not shown]
The secondary outcomes will include the following:

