1. Assess the safety, tolerability, and ease of use of the EyeControl device. This will be achieved by daily review of advance events, and ask patients, families and clinical team regarding challenges of use.
2. Measure the length and intensity of use; We will measure time to first activation, as detailed under the primary goal of the first step, and on a daily basis we will collect data from the device including the number of hours a day the device was worn, how many times it was used for communication, and the type of communication (eg use of predefined sentences, call for help, using new sentences by dictation, entertainment listening etc).
3. Correlate between the monitoring data and clinical data, specifically validate CAM-ICU with nursing and/or study team independent assessment; and correlating wakefulness time with ICU interventions; We will collect from the device on a daily basis the times when the patient has his or hers eyes open, as a marker of wakefulness. We will also record interventions related to sleep and wake cycles, such as administration of

Melatonin or Melatonin agonists, night time antipsychotics, benzodiazepines etc. We will also perform a correlation between the device independent assessment of CAM-ICU, and the clinical team assessment.

- Measure the cognitive and functional long-term outcomes, by phone questioners, to be done in a blinded fashion at 6 months from ICU discharge. This will include a pre-defined battery of tests, as detailed under the Long-Term Outcomes (LTO) Battery section below.

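### The synopsis calls the study blinded-endpoint (PROBE), but no procedure in the protocol masks the CAM-ICU assessments behind the Step 2 primary outcome

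*Combined protocol and SAP*

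**What the plan says.** The Design row of the Synopsis calls the study an "open-label, blinded-endpoint (PROBE) study". The label covers the whole study.

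The Step 2 part of Study Design and Methods builds the primary outcome on CAM-ICU. Its definition begins "Delirium will be defined as CAM-ICU positive, starting at day 1 of use (following the day of training" and runs to day 14 or ICU discharge. The Schedule of Events has CAM-ICU every 12 hours.

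On who performs CAM-ICU:
- Step 1 procedures, item c: "every shift, after the nurse and/or study team member assesses CAM-ICU, the device will repeat the test".
- Step 2 secondary goals (Study Purpose): "the device will assess CAM-ICU independently, and a study team member will repeat this analysis".
- Step 2 secondary outcomes (Study Design and Methods): "specifically validate CAM-ICU with nursing and/or study team independent assessment".

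On the device, the Synopsis says that intervention patients "will keep the device on for as long as they would like". Controls receive standard-of-care communication and no device.

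On blinding, the one endpoint with a stated masked assessment is the long-term telephone battery, a secondary outcome, "to be done in a blinded fashion at 6 months from ICU discharge". Step 1 is expressly unblinded. The Statistical Analysis Plan does not mention blinding.

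**The concern.** CAM-ICU involves judgement and is scored face to face. In an open-label trial, the protection that PROBE offers is that whoever determines the endpoint does not know the arm. If that protection covers only a secondary outcome, the synopsis credits the primary comparison with a safeguard that the methods do not provide, and readers would discount detection bias that is in fact uncontrolled.

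A second gap adds to this. The protocol does not say whether the nurse's, the study team's or the device's CAM-ICU is the result of record. Nor does any rule prevent the study team member who trains a patient on the device from also scoring that patient's primary outcome.

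**Working it through.** **Comparison of the text.** For the label to hold for the primary endpoint, at least one of the following would have to appear.

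| Possible route to a masked CAM-ICU | What the protocol gives |
|---|---|
| Assessor kept unaware of arm | None described; nursing staff or study team only |
| Sham device in controls | None; the comparator is standard of care |
| Headset removed in both arms' routine before scoring | None; wear time is left to the patient |
| Blinded adjudication of recorded results | None |
| Device-administered CAM-ICU as the common measure | Impossible; controls have no device |
| Independent assessment in the Step 2 secondary outcomes | Independent of the device's result, not of treatment arm |

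None of these routes is provided.

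**Scale, as illustration.** The documents give no figure for rater bias, so the shift b below is an assumption.

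Inputs from the Sample Size section: difference 2 days, SD 5.2, power 80%, alpha 0.05, 124 per arm, minimal asymptotic relative efficiency (ARE) of the Mann-Whitney test. Assumed: two-sided testing and an ARE of 0.864, the standard lower bound, since the section states neither.

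1. Reproduce the plan's figure. Per arm, 2 × [5.2 × (1.960 + 0.842) / 2]² = 106.1, or 107 with the t correction. Then 107 / 0.864 = 123.8, rounded up to 124 per arm, so 248 in total. This matches the Sample Size section. The Synopsis gives 244; the two totals should be reconciled, but the present point does not depend on it.
2. Standard error of the between-arm difference: 5.2 × √(2 / (124 × 0.864)) = 0.71 day.
3. With no true effect and a differential scoring shift of b days, the rejection probability is Φ(−1.96 + b/SE) + Φ(−1.96 − b/SE).

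| Assumed shift b (days) | b/SE | False-positive rate |
|---|---|---|
| 0 | 0 | 5.0% |
| 0.25 | 0.35 | 6.4% |
| 0.5 | 0.70 | 10.8% |
| 1.0 | 1.41 | 29.1% |

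Without the ARE factor the SE is 0.66 day, and the last three rates become 6.7%, 11.8% and 32.8%.

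The SD of 5.2 describes delirium/coma-free days in an earlier observational study, not this trial's own outcome. The calculation is a normal approximation and ignores the stratification by ICU in the analysis plan. Masking the assessor would not change the sample size.

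**The case against.** The strongest reply is that this is an omission and not a proven contradiction. Much of it stands as a limit on what can be claimed.

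- A reader might infer that the primary outcome is known to be scored by staff looking at the headset. No sentence says so. It is an inference from in-person assessment with no masking step described.
- The clearest assessor text belongs to Step 1, and Step 2 is called similar only as regards screening and enrolment. The Step 2 text naming the same kinds of assessor concerns validation of the device, not the primary outcome.
- A reader might infer that bedside nurses train patients on the device. The protocol assigns retraining to study staff only.
- A reader might infer a bias in favour of the device. The documents do not settle the direction. The background on delirium says that poor communication can hinder its diagnosis, so better communication could equally lead to more delirium being detected in the device arm.
- Any translation of rater error into days is fragile. CAM-ICU is taken twice a day, and no rule for combining the two readings is given. Suppose that one positive reading makes a delirium day, and that both readings on such a day are truly positive and missed independently. A 20% miss rate per reading then loses only 0.2² = 4% of days.
- Taking the headset off does not mask a nurse who has cared for the patient all shift.

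None of this rescues the label. A study called blinded-endpoint has to say how its primary endpoint is blinded. This one states masking for a different endpoint and is silent on the primary. Followed as written, the plan yields an unmasked primary assessment.

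**Conclusion.** The point holds in this form: the blinded-endpoint description is supported only for the six-month telephone battery. For the Step 2 primary outcome the documents give neither a masking procedure nor an assessor of record, and the one automated source exists in a single arm.

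The documents do not support the stronger reading that biased scoring has been shown, or that it would favour the device by a known amount. The rates of about 11% and 29% rest on assumed shifts of 0.5 and 1.0 day, an SD borrowed from a related outcome, and an assumed ARE of 0.864. They show only that shifts well below the 2-day target difference would matter. Open-label delivery is not criticised. The trial remains analysable, but its design description should be corrected before Step 2 is reported as PROBE.

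**What to change.** 1. **Synopsis, Design.** Limit the blinded-endpoint description to the six-month battery. State that the primary CAM-ICU outcome is assessed without masking, and that detection bias will be acknowledged when the result is interpreted.
2. **Study Design and Methods, Step 2.** Name one CAM-ICU source of record, the same in both arms and not the device. Within existing staffing, have it scored by someone who does not train or retrain that patient.
3. **Optional.** Scoring with the headset off would reduce unmasking but not remove it. If adopted, it must be reconciled with the text that lets the patient decide how long the device stays on.

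The cost is a few sentences, a less favourable design label and some constraint on the rota. The sample size is unaffected.

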## SAMPLE SIZE

From our retrospective analysis (described in the introduction), we expect about 130 patients per month for the initial screening (ventilated for at least two days). The same patient could be ineligible on a certain day, but become eligible later in the admission (e.g., due to the severity of the illness, the patient is deeply sedated for the first few days, and later sedation is weaned). This will allow us to recruit more patients, at different time points of their admission. Even with this in mind, it would be reasonable to assume that about half of these initially screened patients will not be eligible at any point of their admission due to any one of the exclusion criteria. Of those who will be eligible, we expect a high rate of consent, due to the low risk and the potential benefit of using the device while in the ICU. We therefore expect a rate of about 30 patients a month to be enrolled.

For the first step, we will plan to enroll up to 60 patients, and at least a third of the sample will be from the neuroscience ICU, and specifically patients with an acute brain injury

Given that there are no prior data, there is no clear criteria that would justify a specific number. We believe that having 40 to 60 patients work with this new device would be sufficient to draw initial conclusions about its use and specific indications according to the study aims as stated above.

For the second part of the trial, power calculations are based on previously published BRAIN-ICU trial. In that observational trial patients had  $6.8 \pm 5.2$  delirium/coma-free days within the first 14 days of admission, with an overall rate of about 50% rate of delirium. For the present trial, we considered a 2 day reduction in the time spent delirious as clinically significant. Given these parameters, the present trial will require 248 patients ( $N = 124$  per arm) to achieve sufficient power (80%,  $\alpha = .05$ ) to detect a 2 day difference. In general, a sample size of 248 will provide sufficient power to detect a standardized mean difference of 0.38 (assuming minimal asymptotic relative efficiency of Mann-Whitney U test), an odds ratio of 2.14 for binary variables (assuming maximal variance for a binomial distribution), and a Cohen's  $f$  of 0.18.

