### Step 2:

Primary Outcome: The time spent alive and non-delirious in the ICU

Covariates/Confounders: age, gender, race, baseline education level, unit to which the patient was admitted to, need for tracheostomy, severity of illness by SOFA or APACHE score on admission and randomization day, categorical reason for admission (e.g. sepsis, ARDS, elective surgery, stroke etc), diagnosis of delirium prior to randomization and the presence of an acute central neurological injury.

Unadjusted Analyses: The time spent alive and non-delirious in the ICU will be evaluated using the stratified variant of the Mann-Whitney U test. In this analysis, patients will be stratified by ICU setting. For other variables, the unadjusted comparison will depend on the type of variable. In general, continuous variables will be compared using a Mann-Whitney U test and categorical variables will be compared using the  $\chi^2$  test.

Adjusted Analyses: The time spent alive and non-delirious in the ICU will be evaluated using a multi-level/mixed-effects quantile regression (median/50th percentile) while controlling for the previously listed covariates. The multi-level/mixed-effects model will be used to account for clustering within ICU setting. In the event that the regression fails to estimate properly, the covariates will be used to generate propensity scores and patients will be stratified into  $\geq 5$  propensity score strata. The time spent alive and non-delirious in the ICU will then be analyzed using the stratified variant of the Mann-Whitney U test. Analyses of the secondary outcomes will depend on the type of variable. Continuous variables will be analyzed using multi-level/mixed-effects quantile regressions (median/50th percentile), binary variable will be analyzed using multi-level/mixed-effects binary logistic regressions, ordinal scales will be analyzed using multi-level/mixed-effects ordinal (cumulative logit) logistic regressions.

Missing Data: In the event of substantial missing data, data will be imputed using a multiple imputation procedure. The type of procedure (e.g. fully conditional specification, hot decks etc.) and the number of imputed data sets will be determined by the amount of missing data and the pattern of missingness.

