## SUBJECT WITHDRAWAL

In those who wish to discontinue participation, no further data will be collected. Data collected prior to withdrawal will remain in the study database. Those wishing to discontinue participation will also have the informed consent document explained to them, will have any questions answered and will be asked to review and sign an informed withdrawal from the study, however, subjects are not required to complete this document to withdraw. Standard consent procedures will be used. If subjects withdrawal prior to reaching the 30 day outcome visit they will not be counted toward the subject totals in their respective cohort. These subjects will be considered 'incomplete' and coded separately in the electronic database.

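### The Step 2 enrolment target is 244 in the synopsis but 248 in the sample-size section; the plan's own inputs give 248, and the effect on power is small

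*Combined protocol and SAP*

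**What the plan says.** The Enrollment / Duration row of the Synopsis gives "Step 2: 244 Patients, approximately 12 months".

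The Sample Size section bases Step 2 on a published observational ICU cohort with 6.8 ± 5.2 delirium/coma-free days in the first 14 days. It sets the target difference: "we considered a 2 day reduction in the time spent delirious as clinically significant". At 80% power and alpha .05 it concludes that "the present trial will require 248 patients", and it gives 124 per arm. The next sentence uses the same total: "a sample size of 248 will provide sufficient power to detect a standardized mean difference of 0.38", with the qualification "assuming minimal asymptotic relative efficiency of Mann-Whitney U test".

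The planned unadjusted primary analysis fits that basis. In the Statistical Analysis Plan, Step 2, the primary outcome "will be evaluated using the stratified variant of the Mann-Whitney U test", with ICU setting as the stratum.

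The Sample Size section makes no allowance for attrition. The Subject Withdrawal section says of those who leave before a 30-day visit that "they will not be counted toward the subject totals in their respective cohort".

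**The concern.** Both figures are current text for the same randomized step, and they differ by four patients. The document does not derive 244 or connect it to 248. An attrition allowance could not account for the gap, because it would put the enrolment target above the number required, not below it.

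What is at stake is a single pre-specified size for Step 2. The document describes no interim analysis or other stopping rule for this step, so the stated sample size is the only planned end of recruitment. The trial is open-label. With two targets on record, choosing between them during recruitment would be a discretionary decision that the plan does not cover. The Subject Withdrawal rule also refers to subject totals, so staff need to know which total applies.

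**Working it through.** **Inputs from the Sample Size section:** difference 2 days; SD 5.2 days; alpha .05; power 80%; 124 per arm (equal allocation); Mann-Whitney test at its minimal asymptotic relative efficiency.

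**Assumptions, because the document gives no value:** alpha is two-sided; the minimal efficiency is 0.864, the mathematical lower bound relative to the t-test. No adjustment is made for ICU stratification or for withdrawals.

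**Reproducing the plan's figure**

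1. Standardized difference: d = 2 / 5.2 = 0.3846.
2. Two-sample t-test, noncentral t, two-sided .05, 80% power: n = 107.09 per arm.
3. Divide by the efficiency: 107.09 / 0.864 = 123.94, rounded up to 124 per arm, so 2 × 124 = 248.

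The normal approximation also reaches 248 if the t-test size is rounded up first: 107 / 0.864 = 123.8, hence 124 per arm. Other rounding orders move the total slightly. The unrounded normal approximation gives 122.8, hence 123 per arm and 246. Rounding the noncentral-t size up to 108 first gives 108 / 0.864 = 125 per arm and 250. With no efficiency adjustment the total is 214, and a one-sided test without the adjustment gives 168. None of these routes gives 244.

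**Power at the two totals** (effective n per arm = N/2 × efficiency, d = 2/5.2)

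| Efficiency | Power at 244, t (normal) | Power at 248, t (normal) |
|---|---|---|
| 0.864 | 79.4% (79.7%) | 80.0% (80.4%) |
| 0.955 (normal data) | 83.2% (83.5%) | 83.8% (84.1%) |
| 1 (no penalty) | 84.9% (85.2%) | 85.5% (85.7%) |

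At 0.864 the effective sizes are 122 × 0.864 = 105.4 and 124 × 0.864 = 107.1 per arm.

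**Difference detectable with 80% power at efficiency 0.864** (noncentral t)

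- 248: 0.3845, or 0.3845 × 5.2 = 2.00 days.
- 244: 0.3877, or 0.3877 × 5.2 = 2.02 days.

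**Cross-check on the other printed figures.** The section quotes a standardized difference of 0.38. The value at 248 rounds to 0.38 and the value at 244 rounds to 0.39. The normal approximation gives 0.3828 and 0.3859, with the same rounding. The quoted Cohen's f of 0.18 does not discriminate: it is 0.1786 at 248 and 0.1801 at 244.

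**The case against.** A reader might infer that a trial of 244 would be underpowered. The document does not support that in any material sense. The shortfall is 0.6 points by the t calculation. By the normal approximation, 79.7% is 0.3 points below the 80% target. It arises only at the worst-case efficiency; at 0.955 or 1, power at 244 exceeds 80%. The comparison is also finer than the printed inputs allow. With the rounded effect size of 0.38 in place of 2/5.2, the same t method gives 79.1% at 248 and 78.4% at 244, so rounding the effect size moves power about as much as the four patients do. This objection stands.

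A reader might also infer that recruitment would stop at 244. No section says so. The synopsis row is a summary that pairs patient counts with approximate durations, and the justification and per-arm number appear only in the Sample Size section. Four patients are 4/248 = 1.6% of the total. At the expected 30 enrolments a month they amount to about four days of recruitment. With no attrition allowance, ordinary withdrawals could easily exceed four. This also stands, and it limits the point to a correction of consistency.

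The objection does not remove the conflict itself. Two totals remain for one trial step, and only one of them has a derivation.

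**Conclusion.** The Step 2 sample size is stated inconsistently, and 248 (124 per arm) is the supported figure. It follows from the plan's difference, SD, alpha and power, it appears twice in the Sample Size section, and it agrees with the quoted standardized difference of 0.38. That reproduction assumes a two-sided test and an efficiency of 0.864. Rounding order can shift the total to 246 or 250, but no route tried gives 244.

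The consequence for power is under one percentage point at the plan's most conservative efficiency, and at ordinary efficiencies 244 still exceeds the 80% target. The correction is warranted because a trial should have one stated size, whatever the effect on power.

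**What to change.** Change the Enrollment / Duration row of the Synopsis to 248 patients (124 per arm). This is one number, with no effect on design or conduct.

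If 244 is the intended target, leave the Synopsis and restate the Sample Size section as 244 (122 per arm), with about 79% power for the 2-day difference under its minimal-efficiency method. In that case the standardized difference quoted for sufficient power becomes 0.39. The cost is a slightly lower stated power.

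Either way, adding the efficiency value and the sidedness of alpha to the Sample Size section would let a reader reproduce the total without assumptions.
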